6.3. Procedures

6.3.1. Clinical investigation-related procedures

Before initiation of the clinical investigation, sponsor must be provided with key personnel signed and dated curriculum vitae (not more than 2 years old) to verify their qualifications. Key site personnel are those, who treat or evaluate subject data in the clinical investigation. Also, the sponsor will ensure that all site personnel are trained in the investigation procedures, how to complete the CRFs, procedure for reporting an adverse event or serious adverse event (how, when, to whom), and who to contact in case of emergency related to the investigational device.

Study period

Healthy Volunteers:

During the study period, each subject of the healthy volunteers has an information visit and three (3) study visits: Visits 0, 1 and 2. Visit 0 and visit 1 can be the same day.

Information Visit:

Subject will be given information about the investigation by the investigator and have a minimum of 24 hours before deciding on participating in the investigation.

Visit 0 (Inclusion):

Subject will sign the Informed Consent Form (see section 12). It is then ensured that in- and exclusion criteria are met, including urine analysis with multistix, leukocytes and nitrite (Multistix 7, Siemens). Enrolled subjects are allocated a subject number, and hereafter demographics, baseline data and concomitant medication is recorded. A urine sample is collected for baseline data analysis performed by Coloplast laboratory.

Visit 1, 0-7 days after last visit (Normal Voiding):

Subject is asked about symptoms for urinary tract infections (frequent urination, stinging or pain at urination) and a urine analysis with multistix, leukocytes and nitrite (Multistix 7, Siemens) is performed. The subject is asked about use of analgesics up to 24 hours prior to the visit and if the multistix analysis is showing negative in leukocytes and nitrite and there are no symptoms of urinary tract infection and no use of analgesics, the subject will continue with the standard urodynamic examinations (measured twice, first measuring is for adjustment and second measurement is recorded), [REDACTED].

The nurse register relevant data in the CRF, including possible adverse events and relevant concomitant medication. Next visit is scheduled.

Visit 2, 4-15 after last visit (IC)

Subject is asked about symptoms for urinary tract infections (frequent urination, stinging or pain at urination) and a urine analysis with multistix, leukocytes and nitrite (Multistix 7, Siemens) is performed. The subject is asked about use of analgesics up to 24 hours prior to the visit and if the multistix analysis is showing negative in leukocytes and nitrite and there are no symptoms of urinary tract infection and no use of analgesics, the subject will continue with the special urodynamic examination [REDACTED]

In addition, the subject evaluates the discomfort of the insertion and withdrawal of the intermittent catheter using a VAS scale.

The nurse register the subject evaluation and other relevant data in the CRF, including possible adverse events and relevant concomitant medication.

[REDACTED]

The subject has completed the investigation and the termination form is completed.

SCI and BPH patients:

During the study period, each subject of the SCI and BPH population has an information visit and two (2) study visits: Visits 0 and 1.

Information Visit:

Subject will be given information about the investigation by the investigator and have a minimum of 24 hours before deciding on participating in the investigation.

Visit 0 (Inclusion):

Subject will sign the Informed Consent Form (see section 12). It is then ensured that in- and exclusion criteria are met, including urine analysis with multistix, leukocytes and nitrite (Multistix 7, Siemens). Enrolled subjects are allocated a subject number, and hereafter demographics, baseline data and concomitant medication is recorded. A urine culture is performed and antibiotics is prescribed per bacteria present and a urine sample is collected for baseline data analysis performed by Coloplast laboratory. Next visit is scheduled.

Visit 1, 4-15 days after visit 0 (IC):

Subject must be on prescribed prophylaxis antibiotic and is asked about symptoms for urinary tract infections (frequent urination, stinging or pain at urination). A urine analysis with multistix, leukocytes and nitrite (Multistix 7, Siemens) is performed and if there are no symptoms of urinary tract infection, the subject will continue with the special urodynamic examination [REDACTED].

In addition, the subject evaluates the discomfort of the insertion and withdrawal of the intermittent catheter using a VAS scale.

The nurse register the subject evaluation and other relevant data in the CRF, including possible adverse events and relevant concomitant medication.

[REDACTED]

The subject has completed the investigation and the termination form is completed.

6.3.2. Activities performed by sponsor representatives

Sponsor (Clinical Manager or representative hereof) is responsible for:

- Training of investigator and study nurses in the study procedures, how to complete the CRF and how to report possible safety issues to Sponsor. All training will be documented by site and sponsor signing a Training Log
- Analysis of collected Baseline Urine samples
- Bacterial analysis of collected used catheters
- Support during the recruitment process
- Monitoring

No biobank is established. All urine samples in the clinical investigation (baseline data) will be destroyed immediately after laboratory analysis.

6.3.3. Foreseeable factors that may compromise the outcome / results

No foreseeable factors are expected to compromise the outcome/results of the investigation.

6.3.4. Flow-chart

The scheduled visits and corresponding assessments for the period of the investigation is shown I table 4 and 5.

ACTIVITY	INFORMATION VISIT	VISIT 0 (INCLUSION)	VISIT 1 (NORMAL VOIDING)	VISIT 2 (IC)
Subject Oral and written information	X			
Written informed consent		X		
Check of inclusion and exclusion criteria, including urine analysis		X		
Allocation of Subject number		X		
Demographic and Baseline data		X		
Urine sample for measuring baseline parameters		X		
Question subject about use of analgesics 24 hours prior to visit			X	X
Question subject about symptoms of UTI		X	X	X
Urine multistix performed		X	X	X
██			X	X
██			X	
Standard Urodynamic examination performed ██████████ ██ ██ ██			X	
Special Urodynamic examination performed ██████████ ██ ██ ██				X
██				X
██				X
Subject registration of discomfort using a Visual Analogue Scale (VAS).				X
Relevant concomitant medication		X	X	X
AEs/SAEs			X	X
Termination form				X

Table 4 chart showing the connection between visits and assessments for Healthy volunteers.

ACTIVITY	INFORMATION VISIT	VISIT 0 (INCLUSION)	VISIT 1 (IC)
Subject Oral and written information	X		
Written informed consent		X	
Check of inclusion and exclusion criteria, including urine analysis		X	
Allocation of Subject number		X	
Demographic and Baseline data		X	
Urine sample for measuring baseline parameters		X	
Question subject about symptoms of UTI		X	X
Urine multistix performed		X	X
Urine culture performed and antibiotic prescribed per bacteria present		X	
████████████████████			X
██			X
Special Urodynamic examination ██████████ ████████████████████ ████████████████████ ████████████████████			X
██			X
██			X
██			X
Subject registration of discomfort using a Visual Analogue Scale (VAS).			X
Relevant concomitant medication		X	X
AEs/SAEs			X
Termination form			X

Table 5 chart showing the connection between visits and assessments for SCI and BPH patients.

6.3.5. Case Report Forms

All assessments and observations throughout the investigation for each subject must be carefully recorded in the CRF.

The CRFs are printed and supplied by sponsor. The CRFs are printed on NCR paper to have one copy for investigator and one copy for sponsor (original copy). A CRF is provided for each subject. It is the responsibility of the Investigator that all data are entered promptly and correctly.

[figure not shown]
Each CRF has an identification number and a printed instruction for completion.

The sponsor will be responsible for training the investigator and the study nurse in completion of the CRF. The nurse will be responsible for guiding the subject on how to complete the subject's part of the CRF. The CRF will clearly state which parts are to be completed by whom. The subject's part will be the pages regarding discomfort during insertion and withdrawal of the catheter measured by the VAS-scale. These pages will be in Danish. After completion by subject, the study nurse or investigator will measure the VAS-scale and write the measurement in the CRF.

It will be the responsibility of investigator that all measurements and observations are correctly noted with a pen (permanent writing utensil) in the CRF.

Any correction in the CRF must be clearly signed and dated by authorised site personnel. The entry corrected must be crossed out so that the entry is still legible.

Example 1:

Example 2:

[figure not shown]

Figure 1 Two examples of how to make corrections in the CRF

The investigator will keep a separate list with the subject ID numbers, names and addresses in a locked room. Only data referred to in this clinical investigation plan will be recorded in the CRFs.

The sponsor representative(s) will send the CRFs to Coloplast A/S on an ongoing basis after each site visit or as soon as possible after a subject has terminated their last visit.

6.3.6. Concomitant treatment

Healthy subjects may not use analgesics 24 hours prior to catheterisation visits, see inclusion criteria Section 6.2.1

Subjects may not participate in other clinical investigations related to urinary tract system during this investigation, see exclusion criteria Section 6.2.2

Most IC users have bacteria in the urine and to decrease the risk of acquiring a urinary tract infection from the urodynamic examination, urine cultures are performed and prophylactic antibiotics will be prescribed per the result.

6.3.7. Supplementary materials and equipment (if applicable)

Supplementing devices or instruments normally used for catheterisation (e.g. medical gloves, tray for urine collection) and for the urodynamic examinations are supplied by investigator.

The intermittent catheters used in the investigation for measuring endpoints while emptying the bladder with an IC are SpeediCath catheters sponsored by Coloplast A/S. SpeediCath is a CE marked class I, standard sterile catheters intended for intermittent catheterisation of the bladder through the urethra.

6.4. Monitoring Plan

During the period of the investigation monitoring is planned and carried out by the Clinical Manager.

Before doing any review of subject data, the Clinical Manager must review the signed Informed Consent Form(s) and only monitor data from subjects with a correct signed Informed Consent Form.

The first monitoring visit at the site should be conducted as soon as reasonably possible after the first subject at the site has completed the first visit of the investigation to minimise systematic errors done by site.

Additional monitoring will be conducted in accordance to the recruitment rate:

Monitoring visit two (2) will be conducted as soon as possible after the completion of the first 15 subjects

Monitoring visit three (3) will be conducted as soon as possible after the completion of the last 15 subjects

Monitoring visit four (4), Close out visit, will be conducted as soon as possible after database lock

Written informed consent, in- and exclusion criteria and all Adverse events occurring in the investigation will be 100% verified for timely completion for all subjects enrolled in the investigation.

Investigation Site File shall be monitored for 100% completion per the Investigation File Requirement Checklist

Monitoring activities conducted by the clinical manager will be documented in the site visit report applicable to the conducted visit. A summary describing the observation(s) and actions required shall be provided as soon as reasonably possible to the investigator after the conducted monitoring visit.

The sponsor representative will have close contact to the site in the recruitment period to ensure that any concerns, problems or recruitment challenges are solved with the site in a timely manner.

6.4.1. Source data verification

Investigation source data are: the CRFs, Informed Consent Forms, Urodynamic Graphs and tables.

In addition, data completed electronically in Excel-sheets which includes the following data, bacterial analysis and measured discomfort during catheterisation.

All data collected can be directly entered in the CRF and in case site write source data in medical records or nurse notes this will be described in the site specific "Source data specification form"

Only the investigator, delegated site personnel and the sponsor representatives (personnel within Medical Affairs/Clinical Operations) will have access to all the CRFs.

6.4.2. Other methods for data quality assurance

The sponsor, sponsor's representative and/or investigational sites may be inspected by competent authorities or their representatives and likewise may be audited per Coloplast internal quality audit plan and procedures.

7. Statistical considerations

7.1. Statistical design, method and analytical procedures

All statistical analyses described in the protocol are made with SAS version 9.4 (SAS Institute Inc., Cary, NC). Further exploratory analysis might be performed with other software.

Definition of analysis populations

The ITT population (full analysis set) will be constituted by all included subjects who:

- Have provided valid informed consent
- Have valid information for at least one of the endpoints

Invalid individual data points may be omitted from analysis even though the corresponding subject is part of the ITT population. Any exclusion of data points will be documented.

The Safety population (basis for presentation of AEs) will constitute by subjects who have given informed consent.

A formal PP population is not planned due to the explorative nature of the investigation. Considering the data obtained it might however be considered to make additional explorative analyses based on a subset of the ITT population

Analysis of the explorative endpoint

Baseline data will be summarized and listed by type of subject group (spinal cord injury, subjects with enlarged prostate and healthy volunteers) and in total.

For each visit, explorative endpoints will be summarized and listed by type of subject group (spinal cord injury, subjects with enlarged prostate and healthy volunteers) and in total. If the endpoint is a curve ([REDACTED] [REDACTED] only relevant characteristics of the curve (e.g. peak of the curve) will be summarised and listed.

[REDACTED]

If relevant, explorative statistical analyses can be performed.

Adverse events will be listed based on the safety population.

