5.1. Objective

The aim of the study is to explore and understand how urodynamic parameters are affected when emptying the bladder with an intermittent catheter in healthy volunteers, patients with Spinal Cord Injury (SCI) and patients with enlarged prostate (BPH).

The primary objective is to investigate the urodynamic parameters in healthy volunteers emptying spontaneously and with an intermittent catheter (IC).

Secondary objective is to evaluate the urodynamic parameters in spinal cord injured patients as well as patients with enlarged prostate emptying their bladder with an intermittent catheter (IC).

6. Design of the clinical investigation

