2	End points measured during bladder emptying with IC	
 • Check for use of analgesics and symptoms of UTI (and urine multistix performed) • Special Urodynamic examination including flowrate performed (one measurement). Catheters to be used is one standard and one RIK catheter • One hour break • [REDACTED]

- Discomfort registered by subject on a Visual Analogue Scale
- Registration of any adverse events and relevant concomitant medication
- Termination form

Table 1 Study period including three (3) visits, Healthy volunteers

Visit	Process	Activity
-	Study Information	
 • Subject information
0	Inclusion	
 • Informed Consent Form • In- and exclusion criteria fulfilled • Baseline data collected and entered in the CRF by nurse • Relevant concomitant medication recorded • Urine multistix recorded, urine culture performed and antibiotic prescribed per bacteria present • Schedule visit 1 (during treatment with antibiotic) 5-14 days after visit 0
1	Catheterisation with test product 1	
 • Check for symptoms of UTI (and urine multistix performed) • Special Urodynamic examination including flowrate performed (one measurement). Catheters to be used is one standard and one RIK catheter (for SCI pts an extension tube shall be used). • One hour break • Discomfort registered by subject (if possible) on a Visual Analogue Scale • Registration of any adverse events and relevant concomitant medication • Termination form

Table 2 Study period including two (2) visits, SCI and BPH patients

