7.4. Drop-out

Due to the exploratory nature of the study, drop-out subjects will not be replaced.

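### Does section 7.1 need an explicit within-man comparison of catheter and spontaneous emptying in the healthy volunteers?

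*Combined protocol and SAP*

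**What the plan says.** Section 5.1 gives the aim as learning "how urodynamic parameters are affected when emptying the bladder with an intermittent catheter", in healthy volunteers, spinal cord injury (SCI) patients and enlarged prostate (BPH) patients. The primary objective in the same section is narrower: to study the parameters in healthy volunteers under each of the two ways of emptying.

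Under 6.1 and 6.3.1, healthy volunteers are examined during spontaneous voiding at visit 1 and with an intermittent catheter (IC) at visit 2, 4 to 15 days later. SCI and BPH patients have one measurement visit, with IC.

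For the analysis, 7.1 states: "For each visit, explorative endpoints will be summarized and listed by type of subject group". It adds an overall total and reduces curves to their main characteristics. A redacted block follows, and then: "If relevant, explorative statistical analyses can be performed".

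On who is counted:
- The full analysis set in 7.1 takes consenting subjects who "Have valid information for at least one of the endpoints".
- Section 7.1 also says: "Invalid individual data points may be omitted from analysis even though the corresponding subject is part of the ITT population". The next sentence requires any such exclusion to be documented.
- Section 7.4 says that "drop-out subjects will not be replaced".
- At visit 2 (6.3.1), a man needs a negative multistix, and if "there are no symptoms of urinary tract infection and no use of analgesics, the subject will continue with the special urodynamic examination".

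On the catheter, Table 1 says for visit 2: "Catheters to be used is one standard and one RIK catheter". The synopsis and the body of 6.1 speak of a standard IC, and 6.3.7 names SpeediCath as the catheter used for the IC endpoints.

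**The concern.** The aim is phrased as an effect of IC emptying, and only the healthy men supply both conditions. Their within-man difference is the one direct measure of that effect, yet the readable part of 7.1 commits only to describing each visit separately.

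Two things could then go wrong. If the same men contribute at both visits, the by-visit means give the mean difference but not its spread or precision. If different men contribute, because of a missed visit 2 or an omitted data point, the difference between the visit means is no longer the within-man mean difference. With ten men, one missing pair is a tenth of the group. The mention of two catheters in Table 1 could also leave open which measurement serves as the IC value.

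**Working it through.** **1. Figures in the plan.** The group sizes agree with the stated total: 10 + 10 + 10 = 30 (6.2.7, 7.2). Section 7.2 says no formal sample size calculation was done. No SD, effect size or correlation is given, so there is no power or precision figure to reproduce.

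**2. What by-visit summaries leave open.** Let both visits have the same SD, taken as 1, and let r be the within-man correlation (assumed; not in the documents). Then

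- SD of the difference = √(2(1 − r))
- 95% half-width of the mean difference with n pairs = t(0.975, n − 1) × √(2(1 − r)/n), with t = 2.262 for n = 10 and 2.306 for n = 9.

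| r | SD of difference | half-width, 10 pairs | half-width, 9 pairs |
|---|---|---|---|
| 0 | 1.414 | 1.012 | 1.087 |
| 0.5 | 1.000 | 0.715 | 0.769 |
| 0.7 | 0.775 | 0.554 | 0.595 |
| 0.8 | 0.632 | 0.452 | 0.486 |

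Identical by-visit tables fit every row, so the spread of the differences cannot be read from them.

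**3. Comparison with ignoring the pairing.** Treating the visits as two unrelated groups of ten gives t(0.975, 18) × √(2/10) = 2.101 × 0.447 = 0.940. At r = 0.7 the paired interval is 1 − 0.554/0.940 = 41% narrower. At r = 0 it is 1.012/0.940 − 1 = 8% wider. The two are equal at r = 1 − (2.101/2.262)² = 0.14. The plan does not propose the unpaired comparison, so 0.940 is a yardstick and not something the plan would report.

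**4. How many pairs might be lost.** The documents give no drop-out rate. The one relevant figure is in 13.2: urinary tract infection in healthy volunteers is classed as very unlikely, 0-1%. Assume that an infection stops visit 2. At the upper end, the chance that at least one of ten men lacks a pair is 1 − 0.99¹⁰ = 9.6%, and the expected loss is 10 × 0.01 = 0.1 of a man. Moving from ten pairs to nine widens the interval by about 7% (0.769/0.715 = 1.075).

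**5. What the plan already makes available.**
- Section 7.1 promises listings as well as summaries. Subject numbers are allocated at visit 0 (6.3.1). If the listings carry that number, as is usual, each man's two values can be matched and his difference taken.
- Any omitted data point is documented, so the set of complete pairs is known.
- Section 7.1 allows exploratory analyses and analyses on a subset of the full analysis set, and 7.3 fixes 5% for any test. A paired summary in men with both visits falls within these permissions.
- The redacted block lies between the curve sentence and the sentence on optional analyses. A comparison of visits would naturally stand there. The endpoints in 6.1.1 are redacted too, so one cannot see which parameters are measured in both modes. Discomfort is not one of them: Table 4 schedules it at visit 2 only.

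**The case for a change.** The strongest case for a change is that permitted is not the same as promised, and recoverable is not the same as reported. A single sentence in 7.1 would fix the set of men, the IC measurement and the summary before the data are seen. It needs no hypothesis, alpha or sample size, and would cost one table for at most ten men. The exploratory label lowers the stakes but does not remove the logic of pairing.

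The statistical part of this stands: the within-man difference is the natural summary, and the by-visit tables do not contain its precision. The rest is weaker.

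- **Absence is not shown.** The argument needs the redacted block to be silent on pairing, and nobody outside the sponsor can tell.
- **The objectives do not require a contrast.** Values under each mode answer the primary objective as worded. The aim also covers SCI and BPH patients, who have no readable spontaneous measurement, so it cannot mean a within-man contrast throughout. Sections 3, 4.1 and 7.2 describe the use as comparison with laboratory data, building laboratory models and characterisation. Values in each mode serve that use.
- **The catheter point is mostly wording.** The synopsis and the body of 6.1 refer to a standard IC, and 6.3.7 names the product. Only the second catheter in Table 1 is unexplained in readable text. That is a labelling question for the sponsor and does not depend on the pairing.
- **A paired table would not isolate the effect of IC.** Spontaneous voiding always comes first. Visit 1 uses a standard examination done twice with the second recorded, while visit 2 uses a special examination described as one measurement. The difference carries visit order and method along with emptying mode, whether it is tabulated or derived later.

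**Conclusion.** No change to the plan follows. This is at most a gap in readable detail that an analyst would fill sensibly, and the gap may not exist once the redacted text is counted. Followed as written, 7.1 yields correct descriptive summaries in each mode and the individual values from which up to ten within-man differences can be formed. The study has no primary endpoint (6.1.1) and no pass/fail criterion (7.5), so no decision turns on the width of an interval.

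A pre-stated paired table would give a half-width somewhere between 1.01 and 0.45 single-visit SDs for ten pairs, over assumed correlations of 0 to 0.8. The documents do not say where in that range it would fall. The expected loss of pairs from the only documented rate is at most 0.1 of a man.

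The conclusion rests on three assumptions: the listings identify subjects, exclusions are documented as 7.1 says, and losses are not much larger than that rate suggests. A sponsor asked informally could confirm that the paired difference is reported, but nothing in the documents shows that it is missing.
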